Use of anti-diabetic agents other than short-acting insulin for CSII subjects or long-acting insulin for MDI subjects, including: metformin, sulfonylureas, meglitinides, thiazolidinediones, dipeptidyl peptidase 4 (DPP-4) inhibitors, glucagon-like peptide 1 agonists and alpha-glucosidase inhibitors

Statistical Considerations

1. Is stratification/randomization involved? Yes

► IF YES, describe the stratification/ randomization scheme.

During the main study, up to 210 adolescents, ages 12 years - 17 years (inclusive), will be recruited with one of their parent(s)/guardian(s), 18+ y.o., in each arm. Based on experience, approximately 40 adolescents & 40 parent(s)/guardian(s) in each arm will complete the study (N=80 adolescents and 80 parents, total 160 subjects). Male and female adolescents will be recruited, and all racial/ethnic groups will be eligible for participation. Participants will be recruited in randomization blocks of 4. The goal is to target a minimum of 10 participants in each of the 4 stratification subgroups based on age (12-14 y.o and 15-17 y.o.) and insulin therapy (CSII and insulin pen). ,

► IF YES, who will generate the randomization scheme?

Sponsor
 UVa Statistician. Answer/Response:
 UVa Investigational Drug Service (IDS)
 Other: Center for Diabetes Technology (CDT) personnel

2. What are the statistical considerations for the protocol?

The objectives section and the statistical section should correspond, and any objective for which analysis is unfeasible should be deleted. Also, the estimates and non-statistical assumptions of the statistical section should be supported by discussion in the background section.

The answer to this question should include:

-Study Design/Endpoints

- Recap of study objectives and endpoint definitions. An assessment of how study objectives will be assessed by identifying & defining which endpoints will be used to assess each component of the study objectives.
- The study design should include contingencies for early stopping, interim analyses, stratification factors (If applicable), and any characteristics to be incorporated in analyses.
- The power/precision of the study to address the major study endpoint(s), the assumptions involved in the determination of power/precision.

Study Design:

This study employs a randomized design in which one group of participants will be assigned to use the CloudConnect system and the other group to CGM using their insulin paramenters and treatments.

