Study Objectives & Endpoint Definitions:

As mentioned previously, this project seeks to assess how CloudConnect affects participant engagement, dyad engagement, and clinical outcomes in adolescent T1D.

We will assess how adolescents and their parent(s)/guardian(s) respond to this new approach using the Family Communication Inventory (FCI). This diabetes-specific approach was designed by the investigators to assess parent-child communication regarding tasks (discussion of insulin dosing for a given meal, BG trends, need for dose changes). As an outcome measure, scores for parents and adolescents are summed, with higher scores representing higher degree of engagement and T1D-specific communication.

Power/Precision of the study to address major study endpoints:

In using the FCI, we determined based on preliminary data from 220 adolescent/parent participants eligible for the study, with mean (90.3) and standard deviation (12.5) that we are powered to detect a difference of 8.5% in this outcome in the treatment group with 80% power and an alpha of 0.05. This study will require 40 adolescent participants with 40 parent(s)/guardian(s) to complete per arm. Assuming a non-adherence/drop-out rate of 20-30% for Intention-to-Treat (ITT) analysis, 55 participants is yielded per arm.

3. Provide a justification for the sample size used in this protocol.

The study team will attempt to enroll an equal number subjects based on gender, CSII, and MDI use. The study is powered to detect a difference of 8.5% in this outcome in the treatment group with 80% power and an alpha of 0.05. This study will require 40 adolescent participants with 40 parent(s)/guardian(s) to complete per arm. Assuming a non-adherence/drop-out rate of 20-30% for Intention-to-Treat (ITT) analysis, 55 participants is yielded per arm.

4. What is your plan for primary variable analysis?

Because this is a randomized study, our primary outcome (score on the Family Communication Inventory) will be by t-test comparing those randomized to CloudConnect to usual care+CGM. Comparison of secondary outcomes between treatment groups will also be t-tests. Secondary analyses of both the primary and secondary outcomes will utilize multivariable ANOVA, particularly in the event that key variables differ between groups. For example, if average steps per day [as a measure of exercise] is higher in one group vs.

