another, this will be used as a variable in the comparison of mean glucose by CGM to evaluate whether there remained a difference in mean glucose once total daily steps was taken into account. Similarly, if there is an imbalance of key participant characteristics among participants who complete the study in one treatment group (such as higher proportion of multiple-daily-injection participants in the CloudConnect group), this will be considered as a variable in the multivariable ANOVA comparing mean glucose by CGM, as a secondary analysis.

5. What is your plan for secondary variable analysis?

- HbA1c
- Mean glucose by CGM
- Percent time in range 70-180 mg/dL
- Percent time in range 70-150 mg/dL
- Percent time <70 mg/dL
- Percent time >180 mg/dL
- Number of low BG
- Average daily insulin dose
- Average grams of carbohydrate entered
- Steps/day by Fitbit
- Questionnaires: Family Conflict Scale, Division of Diabetes Responsibilities, Child Self Management and My-Q scores.
- Response to weekly standardized questions:
 - i. *During the past week, did you talk with your parents about your diabetes management?*
(Yes=1, No=2)
 - ii. If you answered “yes,” how good or bad was the tone of that conversation?
(Likert scale: Very good = 1; good =2; Neutral = 3 bad =4; Very bad =5)
 - iii. During the past week, did you change your insulin parameters?
(Yes=1, No=2)

6. Have you been working with a statistician in designing this protocol?

No

7. Will data from multiple sites be combined during analysis?

No

Study Procedures-Biomedical Research

1. What will be done in this protocol?

PILOT STUDY:

Up to six adolescent subjects and six parent(s)/guardian(s) will be enrolled in a Pilot Study to assess the components used by the Experimental Group of the Main Study. This trial will evaluate if: (i) subjects can be trained to use study CGM + study Fitbit + personal pump (if pump user) or study insulin pen for mealtime

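### Age group and insulin therapy are named as stratification factors, but the planned t-tests ignore them; insulin therapy appears only as an example covariate if completers are imbalanced, and age not at all

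*Combined protocol and SAP*

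**What the plan says.** All references are to the Statistical Considerations section of the combined protocol and SAP.

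- **Item 1 (stratification and randomization)** describes "4 stratification subgroups based on age (12-14 y.o and 15-17 y.o.) and insulin therapy (CSII and insulin pen", with a goal of at least 10 participants in each. On blocking it says: "Participants will be recruited in randomization blocks of 4". It does not say outright that the blocks are formed within the four subgroups.
- **Item 3 (sample size)** says: "The study team will attempt to enroll an equal number subjects based on gender, CSII, and MDI use". Gender is new here and age is absent.
- **Item 4 (primary variable analysis)** says "our primary outcome (score on the Family Communication Inventory) will be by t-test comparing those randomized to CloudConnect to usual care+CGM", and then "Comparison of secondary outcomes between treatment groups will also be t-tests". No stratification factor is in either comparison.
- **Item 4, adjusted analyses**: "Secondary analyses of both the primary and secondary outcomes will utilize multivariable ANOVA, particularly in the event that key variables differ between groups". One trigger is given as "if there is an imbalance of key participant characteristics among participants who complete the study in one treatment group". The example is a "higher proportion of multiple-daily-injection participants in the CloudConnect group", and the outcome in that example is mean glucose by CGM.

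Age group is not named as a covariate in any analysis.

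**The concern.** Stratified allocation forces the arms to be alike on the strata, so differences between strata no longer contribute to chance variation in the treatment difference. A two-sample t-test does not know this. It leaves the between-stratum variance in its standard error, which gives intervals that are too wide and p-values that are too large whenever the strata predict the outcome.

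Observed imbalance is also the wrong trigger for adjustment. Stratification is meant to prevent imbalance on insulin therapy, so a rule that waits for it would seldom bring that factor into the model. The reason to include the factor is that it was used to randomise and may predict the outcome.

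At stake is precision that the design has already paid for, in a trial whose 40 completers per arm fall slightly short of the stated power. The differing lists in items 1 and 3 also leave a reader unsure which factors govern allocation.

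**Working it through.** **Inputs.** FCI mean 90.3, SD 12.5, difference 8.5%, 80% power, alpha 0.05 and 40 completers per arm (item 2). Blocks of 4 and four strata (item 1). Alpha is assumed two-sided. The share of outcome variance explained by the strata, R², is not in the documents, so 0% to 30% is assumed.

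**Step 1: reproduce the plan's figure.**
- Difference = 0.085 × 90.3 = 7.68 points.
- n per arm = 2 × (1.960 + 0.842)² × (12.5 / 7.68)² ≈ 41.6, so 42, against 40 stated.
- At 40 per arm, SE = 12.5 × √(2/40) = 2.795 and 7.68 / 2.795 = 2.746. Power = Φ(2.746 − 1.960) = 78.4%, or 77.4% by the exact t distribution.

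The stated figure is reproduced closely. It uses the total SD and a plain two-group comparison, so it takes no credit for stratification.

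**Step 2: blocks within strata, exact balance.** The true SE of the difference is 2.795 × √(1 − R²), while the t-test still reports about 2.795. Hence:
- SE ratio = 1 / √(1 − R²)
- type I error = 2 × [1 − Φ(1.960 / √(1 − R²))]
- unadjusted power = Φ((2.746 − 1.960) / √(1 − R²))
- adjusted power = Φ(2.746 / √(1 − R²) − 1.960)

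Example at R² = 20%: √0.8 = 0.894, 1.960 / 0.894 = 2.191, and type I error = 2 × [1 − Φ(2.191)] = 2.8%.

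Brackets show a simulation of 40,000 trials per setting (four strata of 20, 10 per arm in each), which uses the t distribution.

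| Assumed R² | SE ratio | Type I error, t-test | Power, t-test | Power, strata in model |
|---|---|---|---|---|
| 0% | 1.00 | 5.0% (5.1%) | 78.4% (77.4%) | 78.4% (77.3%) |
| 5% | 1.03 | 4.4% (4.4%) | 79.0% (78.1%) | 80.4% (79.4%) |
| 10% | 1.05 | 3.9% (3.9%) | 79.6% (78.7%) | 82.5% (81.8%) |
| 20% | 1.12 | 2.8% (3.0%) | 81.0% (79.7%) | 86.7% (85.7%) |
| 30% | 1.20 | 1.9% (1.9%) | 82.6% (80.8%) | 90.7% (89.6%) |

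**Step 3: allow for dropout.** The plan's 55 per arm implies 1 − 40/55 = 27% loss, which breaks exact balance among completers. Simulating 110 dyads in blocks of 4 within strata, with 27% random dropout, gives a t-test type I error of about 4.5%, 4.1%, 3.4% and 2.7% at R² of 5%, 10%, 20% and 30%. Repeat simulations gave values up to about 0.4 points higher. The distortion shrinks but does not vanish.

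**Step 4: blocks not within strata.** Simulated type I error of the t-test stays near 5% at every R². Adjustment still helps: power is about 80%, 85% and 89% at R² of 10%, 20% and 30%, against about 77-78% unadjusted. At 5% it roughly breaks even, and at 0% it costs about 2 points.

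**The case against.** The strongest reply is that the planned analysis is valid. Any error is conservative, false positives are not inflated, and adjusted analyses are already foreseen as secondary. The size of the effect rests on an R² that no document supplies, and the standard-error argument needs blocks within strata, which item 1 does not state. All of this stands. It limits the point to a gain in precision and a clarification.

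Four stronger readings are tempting, and the documents do not support them.

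- **A reader might infer that the stated power is lost.** It is not. The 80% was computed from the total SD for an unadjusted comparison, and under stratified allocation the t-test's power stays level or rises slightly (Step 2). Only the further gain from adjustment is forgone.
- **A reader might infer two rival allocation schemes**, one by age and therapy, the other by gender and therapy. Item 3 is worded as an enrolment aim within the sample-size justification. It can coexist with item 1, and no text describes a gender-by-therapy stratification.
- **A reader might infer that the ANOVA is run only after an imbalance.** Item 4 says it applies particularly in that event, which is not exclusively. The conditional wording fits the insulin-therapy example.
- **A reader might infer that the glucose outcomes suffer most.** The calculations cover only the FCI, and the documents give no R² for any outcome.

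**Conclusion.** The point holds as a low-cost improvement. The factors named for stratification are absent from the primary and secondary comparisons, and making adjustment for insulin therapy depend on observed imbalance is weak practice.

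If blocks run within strata, the t-test is conservative by an amount that depends on R². Type I error falls from 5% to about 4.4% at R² of 5% and about 1.9% at 30% under exact balance, or to about 4.5% and 2.7% with 27% random dropout. By simulation under exact balance, the power forgone is about 1, 3, 6 and 9 points at R² of 5%, 10%, 20% and 30%. If blocks do not run within strata, the conservatism disappears, but most of the power gain remains once the strata explain about 10% or more of the variance. If the strata predict nothing, nothing is lost.

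These sizes assume a two-sided test, 40 completers per arm, a 7.68-point difference, equal-sized strata in the exact-balance case and dropout unrelated to outcome.

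**What to change.** 1. In item 4, replace the plain t-test for the primary and continuous secondary outcomes with a linear model containing arm, age group (12-14, 15-17) and insulin therapy (CSII, pen), fitted whether or not the arms look balanced.
2. Delete observed imbalance as the trigger for including insulin therapy.
3. In item 1, state whether the blocks of 4 are applied within the four strata, and say so plainly if that is what is done.
4. In item 3, label gender as a recruitment aim only, so that one list of stratification factors remains.

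**Cost.** Wording only, since both factors are known at entry. The model uses 2 degrees of freedom for the two factors, or 3 if the four strata are fitted separately, out of 78. If the strata predict nothing, the loss is about 0-1 point of power with blocks within strata, and about 2 points without.

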Both groups will participate in the same number of visits (completed either in clinic or via phone or video conferencing) and follow up communication contacts done by phone calls, text messages and/or emails during the entire length of the trial. The production of the CloudConnect Report, in combination with the available Dexcom alarms and apps, is the study differential between groups.

*Secondary health outcomes: Average Blood Glucose values by Continuous Glucose Monitor; average total daily insulin; average carbohydrate of grams entered; number of insulin boluses; average number of steps by day

Figure 1: Study Design

There are four visits in the Main Study. Visit 1 and 2 may be combined and may be in person or via phone or video conference. A repeat Hemoglobin A1c will be collected if visit 1 and 2 are greater than 28 days. Visit 3 may be completed by phone. In addition, there will be weekly communication done by phone call, text message and/or email throughout the entire 12 weeks (3 months) of the data collection portion of the study. Method of weekly communications with the adolescent and parent will be based on participant/parent preference. The study team will communicate separately with the child and the parent in order to obtain their feedback independent of the other.

Subjects will be asked to electronically complete the following questionnaires at the completion of Visit 1 and repeated again at the conclusion of their study participation. Questionnaires may be answered remotely (i.e. at home) within a week of the visit or during a CRU visit.

- Blood Glucose Monitoring Communication questionnaire (Hood et al Diab Care 2004)
- Child and Parental Responsibility Questionnaire (adapted from Anderson et al J. Ped Psychol 1990)
- Child Self-Management
- Diabetes Care and Communication
- Diabetes Family Conflict Scale-Revised (Hood et al Diab Care 2007)
- Family Communication Inventory

- MY-Q (deWit et al Ped Diab 2012)
- Questions about CloudConnect use (CloudConnect group only, asked only at study end):
 - On a scale of 1-7, with 1 being very difficult and 7 being very easy, how easy was it to understand the information provided in the weekly reports? Can you tell me why you gave the score you did? What could have made the weekly reports easier to understand?

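### The primary t-test needs both FCI scores from a dyad, and the plan has no rule for a dyad with only one, so a collected score goes unused

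*Combined protocol and SAP*

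**What the plan says.** Statistical Considerations, item 2 (Study Objectives & Endpoint Definitions), builds one value per dyad: "scores for parents and adolescents are summed, with higher scores representing higher degree of engagement and T1D-specific communication". Item 4 gives the analysis: "our primary outcome (score on the Family Communication Inventory) will be by t-test comparing those randomized to CloudConnect to usual care+CGM". The multivariable ANOVA in items 4 and 5 is secondary, is meant for imbalance between arms, and has no stated role for missing scores.

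The sample size in item 2 is counted in pairs: "This study will require 40 adolescent participants with 40 parent(s)/guardian(s) to complete per arm". It is raised to 55 per arm for 20–30% non-adherence and dropout. Intention-to-treat is named only in that inflation.

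Study Procedures, Main Study, schedules the FCI at Visit 1 and at the end of participation only, and says: "Questionnaires may be answered remotely (i.e. at home) within a week of the visit or during a CRU visit". Withdrawal for non-compliance (Subject Compliance with Study Procedures) depends on missed device downloads, not on questionnaires. No section gives proration, imputation, a per-respondent primary analysis or any other rule for a dyad with one FCI score.

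**The concern.** A sum is undefined when one part is missing, and a two-sample t-test needs one value per unit. A dyad can stay in the trial, supply its downloads, count as a completer, and still have only one week-12 FCI score. The planned test then uses nothing from that dyad.

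Two things are at stake. The first is precision, because each half-observed dyad costs a full unit although part of its outcome is known. The second is selection. The trial is open-label and measures engagement, and not answering a questionnaire is plausibly a sign of low engagement. If non-response differs between arms, a comparison restricted to complete dyads can be biased. A rule chosen after seeing which scores are missing would be open to challenge.

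**Working it through.** **Inputs from the protocol (Statistical Considerations, item 2).** FCI mean 90.3 and SD 12.5; "powered to detect a difference of 8.5% in this outcome in the treatment group"; "with 80% power and an alpha of 0.05"; 40 completing dyads per arm, 55 after inflation.

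**Assumptions, not in the documents.** Two-sided test; 12.5 is the SD of the dyad sum; non-response p per person at week 12; parent–adolescent score correlation ρ from 0.2 to 0.7, with equal variances.

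**1. The plan's own figure.** Difference = 0.085 × 90.3 = 7.68 points; d = 7.68/12.5 = 0.614. By normal approximation, n = 2(1.960 + 0.842)²/0.614² = 41.6, so 42 per arm. Power at 40 per arm is 0.784 by normal approximation and 0.774 by noncentral t. The stated 40 is reproduced closely, with no slack. Since 1 − 40/55 = 27.3%, the 55 lies inside the stated 20–30%.

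**2. Dyads left for the t-test.** With independent non-response, the share with both scores is (1 − p)² and the share with exactly one is 2p(1 − p). At p = 0.10 these are 0.81 and 0.18.

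**3. Joint model of both scores.** Each complete dyad contributes the inverse of the 2×2 correlation matrix, and each half-observed dyad contributes one diagonal element. For the arm mean of the sum this gives

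n_eff = n[(1 − p)² + p(1 − p)(1 + ρ)].

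At n = 40 and p = 0.10: 40(0.81 + 0.09 × 1.2) = 36.7 for ρ = 0.2, and 40(0.81 + 0.09 × 1.7) = 38.5 for ρ = 0.7.

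**4. Power (noncentral t, d = 0.614).**

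| Dyads per arm before non-response | p | Complete dyads | Power, t-test on sum | n_eff, joint model | Power, joint model |
|---|---|---|---|---|---|
| 40 | 5% | 36.1 | 0.73 | 38.4–39.3 | 0.76–0.77 |
| 40 | 10% | 32.4 | 0.68 | 36.7–38.5 | 0.74–0.76 |
| 40 | 15% | 28.9 | 0.63 | 35.0–37.6 | 0.72–0.75 |
| 55 | 10% | 44.6 | 0.82 | 50.5–53.0 | 0.86–0.88 |

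The rows at 40 suppose that withdrawals have used up the whole allowance. The row at 55 supposes no withdrawals at all. The joint-model figures treat the covariance as known and take no credit for baseline scores.

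**5. Non-response clustered within dyads.** Take p = 0.10 and a within-dyad correlation of non-response of 0.5. Both members are missing in 0.01 + 0.5 × 0.09 = 5.5% of dyads, exactly one in 2(0.10 − 0.055) = 9%, and neither in 85.5%. At 40 per arm, 34.2 dyads are complete (power 0.71). The joint model has n_eff = 40[0.855 + 0.045(1 + ρ)] = 36.4 to 37.3 (power 0.73–0.74). The gain is about 3 to 4 points.

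**6. If 90.3 and 12.5 describe one respondent.** The difference in the sum is 0.085 × 180.6 = 15.35 and its SD is 12.5√(2(1 + ρ)), so d = 0.79 (ρ = 0.2) to 0.67 (ρ = 0.7). Power with 32.4 complete dyads is then 0.88 to 0.75.

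**The case against.** The strongest reply is that the documents are silent rather than wrong. A reader might infer that the plan excludes half-observed dyads. No section says so, and a t-test on the sum is compatible with imputing the missing half. That stands: exclusion is only what results when the stated outcome and test are applied with nothing added.

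A reader might also infer that the trial's power is really 68%. The documents do not support that. They give no questionnaire non-response rate, and the 20–30% allowance may already cover some of it. From 55 per arm, 10% non-response as the only loss still leaves more than 40 complete dyads. Step 6 shows that the figure also depends on an unstated scale.

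Nor do the documents support a loss of dyads at about twice the individual non-response rate. That needs independence, whereas parent and adolescent share the Visit 4 occasion to which the end questionnaires are tied. The Main Study section also has both members available for contact about completing questionnaires, which should reduce non-response.

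Finally, if the silent member is silent because of low engagement, the missingness may depend on the unseen score. A model that assumes missingness at random does not cure that. This stands too, and it limits what the fix can claim.

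None of this supplies a rule for a dyad with one score.

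**Conclusion.** The point holds as a gap with a concrete better method available. The primary outcome is a two-person sum, the test needs the whole sum, and a half-observed dyad has no stated handling. The mechanism is certain; its size is not. Under independent 10% non-response and an SD of 12.5 for the sum, the joint model gains about 5 to 8 points of power at 40 per arm and 4 to 6 points at 55. Clustering of non-response reduces the gain at 40 to about 3 to 4 points. As to bias, the joint model removes only the part explained by observed scores. The documents support neither a claim that the trial is underpowered for this reason nor a claim that the joint model would remove selection bias.

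**What to change.** Make the primary analysis a linear mixed model of the parent and adolescent week-12 FCI scores, two outcomes per dyad:

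- terms for respondent, arm and respondent-by-arm, with unstructured within-dyad covariance;
- both members' Visit 1 FCI scores as covariates;
- every dyad with at least one week-12 score included;
- the arm difference in the sum (parent contrast plus adolescent contrast) as the primary effect, with both components reported;
- the complete-dyad t-test kept as a sensitivity analysis.

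State how a missing baseline score is handled, so that the covariates do not drop the same dyads again. Visits 1 and 2 may be combined and questionnaires may follow within a week, so the plan should also require the baseline FCI before randomisation. State whether 90.3 and 12.5 refer to the dyad sum or to one respondent.

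The target remains the plan's own. Without the baseline covariates and with no missing scores, the estimate equals the t-test's difference in means; with them it is an adjusted estimate of the same difference.

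The cost is plan wording, slightly more analysis work and the baseline timing rule, with no new data. The downside is the assumption of missingness at random given the other member's score and baseline.
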